Lallemand Solutions Santé [name] [name] Coordination Centre de recherche du CHUS [name]. [name], Data manager

Authorized and approved by Trial steering and management committeeNameSignatureDate

Section 2: Introduction

7. Background and rationale

Probiotics may be considered as an option of treatment for long COVID since they have anti-viral effect, trigger immunomodulation and have low side-effects. This randomized controlled trial aims to reduce the number of patients with long COVID by 25% 90 days after the COVID-19 diagnosis by taking probiotics in a symptomatic population, self-caring at home. During the acute phase of the disease, participants will take two capsules (probiotics or placebo) per day for 10 days and one capsule (probiotics or placebo) per day for the following 15 days. A follow-up will be done twice during the acute phase, 14 days and 28 days after starting to take the investigational product (compliance to treatment, side effects, etc.). At inclusion and at Day14, Day30 and Day90 after the COVID-19 diagnosis, a questionnaire will be administered (COVID-19 symptoms, anxiety, functioning difficulties, etc.) and 2 saliva (microbiota analyzes) self-samples will be performed.

COVID-19 disease caused by a new coronavirus (SARS-CoV-2) has received worldwide attention. No effective treatment against COVID-19 is available and the current vaccination appears essential to control the pandemic. However, many questions remain, such as the durability of immunity and the appearance of variants. While the acute phase has been widely studied, the long-term consequences are unknown, and a new burden is emerging: the long COVID. The long COVID is defined by the persistence of symptoms of the disease for more than 4 weeks after diagnosis. Several strong arguments support the study of probiotics for COVID-19: 1) probiotics act on viruses by various well described mechanisms (reduction of absorption, cellular internalization of the virus, production of metabolites/substances having a direct antiviral effect and immunomodulation); 2) probiotics are considered with a high level of evidence (meta-analysis) to reduce diarrhea (associated with antibiotics and Clostridium difficile) and for respiratory tract infections and 3) probiotics are affordable and available with low side-effects.

8. Study Objectives

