We reviewed the participants who showed a moderate level or more ([2:3]) at D30 and D90 for difficulty performing current activities, pain/comfort and anxiety/depression. Worsening of Functioning difficulties:

For the functioning difficulties, participants were asked to estimate their functional status before COVID-19 in the form at D30 and in the form at D90. The smaller value was retained if an inconsistency was detected between these two values. We harmonized the recorded values pre-COVID-19 at D30 and D90. We selected participants with a non-zero value at D30 and a difficulty value at D90 higher than pre-COVID-19 for Concentration and memory, and the ability to Take

care of themselves.

The status of FLU-PRO and quality of life indicators before COVID-19 disease was initially unknown. Thus, we have operationalized the WHO's definition to select patients. If at least one of the criteria was met, the participant would be qualified for an expert's review. Every diagnosis based on Binomes was reviewed by expert on LONG-COV physicians. Those initially selected who potentially qualified for LONG-COV were called after the study to verify if symptoms were present or not before the positive detection of COVID-19. The final decision was on the expert physician responsibility.

First, initial analyses were carried out using a binary LONG-COV criterion (yes/no). Secondly, LONG-COV cases were categorized according to their level of severity and symptoms profile over time. Participants in the intervention and the placebo arms of the trial were compared.

21. Descriptive analyses of outcome measures

Distribution of score measures will be calculated for each of: COVID-19 symptoms (FLU-PRO and loss of smell and/or taste), quality of life indicators (GAD-7) and functioning difficulties (WG-SS) at D30 and D90 timepoints. The distributions will be generated overall and comparatively by intervention arm using t-test or rank sum testing as appropriate based on the distributions.

Individual symptom frequency for those items included and not included in the FLU-PRO instrument score will be described and compared between groups using chi-squared or fishers exact tests as appropriate.

22. Stratifying variables

The analysis will follow the randomization strategy. Gender and age were used as stratifying variables. We will use the same categories in the analysis.

23. Primary outcome analyses

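### Section 21 compares scores and symptoms between arms without the randomisation strata that Section 22 says the analysis will use, and without the inclusion scores: a minor, free gain in precision

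*SAP*

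**What the plan says.** SAP Section 21, headed as descriptive, covers symptom scores (FLU-PRO with smell and taste), GAD-7 and "functioning difficulties (WG-SS) at D30 and D90 timepoints". Distributions are produced overall and "comparatively by intervention arm using t-test or rank sum testing as appropriate based on the distributions". Individual symptoms are to be "described and compared between groups using chi-squared or fishers exact tests as appropriate"; that sentence gives no time point. Section 21 mentions neither strata nor inclusion scores, and gives no rule for choosing between the tests.

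Section 22 follows directly: "The analysis will follow the randomization strategy. Gender and age were used as stratifying variables. We will use the same categories in the analysis". Section 10 defines four age bands and two genders, so there are 8 strata.

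Inclusion values are collected. Section 7 says: "At inclusion and at Day14, Day30 and Day90 after the COVID-19 diagnosis, a questionnaire will be administered", and lists symptoms, anxiety and functioning among its contents.

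Sections 23 and 24 do stratify. LONG-COV status is compared by CMH (primary and S1), and strata indicators enter the LONG-COV GEE. The S2 GEE models symptom severity over all time points with baseline characteristics.

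**The concern.** Section 21 carries a descriptive heading but names hypothesis tests, and Section 11 sets alpha at 0.05 unless otherwise specified. Section 17 shows that the SAP can rule out testing when it means to, since it does so for the baseline table. So p-values should be expected from Section 21, and on a plain reading they do not follow Section 22.

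Two separate matters are involved. The first is internal consistency: the strata are promised and not used. The second is efficiency: the inclusion scores are available and not used, though the SAP never said they would be. At stake are the precision and calibration of secondary comparisons. For GAD-7, WG-SS and individual symptoms no adjusted between-arm analysis is named elsewhere, so the Section 21 test is the only one a reader will see.

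**Working it through.** **1. The plan's own figure.** Section 11 gives 50% versus 37.5%, two-sided alpha 5% and power 80%. With pooled variance, the number per group is

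[1.960·√(2·0.4375·0.5625) + 0.842·√(0.5·0.5 + 0.375·0.625)]² / 0.125² = (1.375 + 0.586)² / 0.015625 ≈ 246.1, rounded up to 247.

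That gives 494 in total, and 494 / 0.80 = 617.5, rounded up to 618. The stated size is reproduced. It belongs to the primary comparison and is not touched by this point.

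**2. Leaving out the strata.** Let the strata explain a share R² of the outcome variance, and suppose that stratified randomisation balances them closely. The unadjusted test uses a standard error based on the full variance, while the true variance of the arm difference is smaller by the factor 1 − R². Then

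- true alpha = 2·[1 − Φ(1.960/√(1 − R²))]
- power, where the stratified test has 80%, = Φ(2.802 − 1.960/√(1 − R²)), with 2.802 = 1.960 + 0.842.

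| Assumed R² | 1.960/√(1 − R²) | True alpha | Power |
|---|---|---|---|
| 5% | 2.011 | 0.044 | 78.5% |
| 10% | 2.066 | 0.039 | 76.9% |
| 20% | 2.191 | 0.028 | 72.9% |

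The SAP gives no R²; the range is an assumption.

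**3. Leaving out the inclusion score.** With correlation r between inclusion and follow-up score, a linear model multiplies the variance of the mean difference by 1 − r². The flow-chart counts at D90 (Section 16) are 239 and 240. The effect detectable with 80% power, in SD units, is 2.802·√(1 − r²)·√(1/239 + 1/240) = 0.256·√(1 − r²).

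| Assumed r | Variance factor | Detectable effect | Power at 0.25 SD |
|---|---|---|---|
| 0 (unadjusted) | 1.00 | 0.256 SD | 78% |
| 0.3 | 0.91 | 0.244 SD | 82% |
| 0.5 | 0.75 | 0.222 SD | 89% |

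The SAP gives no r either. The formula applies to a linear comparison of means, not to the rank sum, chi-squared or Fisher tests. The gains in steps 2 and 3 overlap and should not be added.

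**4. Choosing the test from the data.** A null simulation used 240 per arm, 4,000 replicates, and normal, lognormal and skewed-count scores. Choosing by a normality pre-test gave a false-positive rate of 0.051 to 0.059. The upper value is also what the rank sum test alone gave for the same skewed counts, so the choice itself added nothing there. Reporting the smaller of the two p-values gave 0.060 to 0.083.

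**5. What other sections already cover.**

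| Outcome | Adjusted between-arm analysis named |
|---|---|
| LONG-COV status | Yes: CMH, and a GEE with strata indicators |
| Symptom severity | Yes: S2 GEE with baseline characteristics |
| GAD-7, WG-SS | None |
| Individual symptoms | None; S1 gives a table |

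**The case against.** The best defence is that Section 22 introduces Section 23 and governs the efficacy analyses, which are in fact stratified, while Section 21 only describes. That reading is possible. But Section 22 speaks of the analysis without limit, and Section 21 prescribes tests, so the text needs a clarifying sentence either way.

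The defence also limits the point, and these limits stand. A reader might infer any of the following, and the SAP supports none of them:

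- **That Section 22 promises adjustment for inclusion scores.** It names gender and age only.
- **That the unadjusted comparisons are biased or raise false positives.** Randomisation protects against bias, and ignoring balanced strata makes the tests conservative.
- **That the results will conflict with the CMH and GEE analyses.** CMH is specified for LONG-COV status, and the GEE models a trajectory over time. Different outcomes and estimands may give different p-values without conflict.
- **That the gain is worth a third more participants.** That figure is 1/0.75 at r = 0.5. Everyone is symptomatic and within 10 days of diagnosis at inclusion (Section 9), so the inclusion symptom score reflects acute illness and may correlate only weakly with D90.
- **That the open choice of test inflates alpha.** Choosing by distribution left it near nominal. The inflated range comes from picking the smaller p-value, which the SAP does not propose, and its opening section keeps the analysis blinded to group. What remains is that no criterion is stated, so whether means or ranks are compared is left open.

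**Conclusion.** The point holds as a minor one. The Section 21 tests leave out strata that Section 22 says will be used and, as a separate efficiency matter, leave out inclusion scores that the trial collects. There is no bias, and the primary analysis and sample size are unaffected.

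The cost is some precision and mild conservatism: alpha of about 0.044 to 0.028 for an assumed R² of 5 to 20%, and a variance reduction forgone of 9 to 25% for an assumed r of 0.3 to 0.5 in linear mean comparisons. The alpha figures also assume that the randomisation lists balance the strata closely. The practical gap is GAD-7, WG-SS and individual symptoms, since the S2 GEE already addresses symptom severity.

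**What to change.** Choose one of two routes and say so in Section 21.

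- **Keep the comparisons.** For each score compared by arm, prespecify one linear model of the D30 or D90 score on arm, inclusion score, age stratum and gender, with robust standard errors and a 95% confidence interval. Compare individual symptoms by CMH over the same age and gender strata, and state the time points. Section 7 names domains rather than instruments, so confirm that GAD-7 and WG-SS are the instruments used at inclusion.
- **Drop the p-values.** Report distributions and frequencies by arm only, so that Section 21 matches its heading.

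Either route removes the inconsistency with Section 22 and the open choice of test. The cost is a few lines of SAP text, an entry in the revision table of Section 5, and simple programming on data already collected. If these analyses have already been run, report the adjusted version as a declared deviation, as the SAP's opening section provides.

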A table describing the demographic and clinical characteristics at baseline randomization will be generated, however statistical testing will not be done comparing individual variables between groups.

Participation in follow-up assessments and completeness of outcome data will be calculated and compared for each time point by study arm. A sensitivity analysis on loss to follow-ups will be performed using weights or extreme case scenarios. In the latter method, we will assume that all losses to follow-up had or did not have LONG-COV at D90, enabling us to estimate the potential bias.

18. Intention to treat

For the primary analyses, we will follow an intention to treat model. All participants will be assigned intervention status based on their randomized assignment. We will use an inverse probability of censoring for missing outcome data. Participants lost to follow-up will be censored.

19. Adherence per protocol analysis

Per-protocol analyses will include all participant randomized to either control or intervention arm, excluding participants lost to follow up or those non-adherent to the assigned intervention. Adherence will be estimated via self-reported adherence in the logbooks at D14 and D28 completed online or on paper (according to the preference of the participant). If at least 80% of the doses prescribed was taken i.e. 20 pills out of 25, we consider that the participant adhered to the protocol.

20. Long-term COVID-19 (LONG-COV)- Outcome definition

Background

Based on the WHO, long-term COVID is defined as follows: "It is defined as the continuation or development of new symptoms 3 months after the initial SARS-CoV-2 infection, with these symptoms lasting for at least 2 months with no other explanation. »

(https://www.who.int/europe/news-room/fact-sheets/item/post-covid-19-condition)

Definition of COVID-LD in PROVID-LD

Long-term COVID-19 (LONG-COV) status was defined according to three criteria:

A Binome of COVID-19 symptoms from FLU-PRO:

A binome is a recurrent symptom, i.e. present at D30 and D90. We selected participants with at least one symptom recorded at D30 and D90 with a value of moderate level or more ([2:4]). Also, we selected the participants who presented the symptoms of "Loss of Taste" and/or "Loss of Smell" at D30 or D90.

A Binome of symptoms from the Quality of life indicators:

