The proportions of participants with LONG-COV at D90 will be compared using the Cochran-Mantel-Haenszel test, adjusting for stratification.

24. Secondary outcome analysis

S1: The presence and severity of symptoms at D14, D30 and D90 will be explored by doing a descriptive analysis for each study-time. The proportions of participants with LONG-COV at D14, D30 and D90 will be compared using the Cochran-Mantel-Haenszel test, adjusting for stratification. A table will summarize the proportion of each symptoms at each time with the means severity per study arm.

S2: A GEE analysis (with linear or logit link function depending on the variables) will use Symptoms Severity as the outcome over all time points and include baseline characteristics. This is to assess whether the intervention reduces the number and severity of symptoms. A faster decrease is expected with intervention.

We will supplement these analyses with a GEE (with a logit link function), using a binary LONG-COV status as the outcome and including measurements at Baseline, D14, D30 and D90 and indicator variables for stratification.

If there are differences in censoring by group, an additional GEE model will be used with inverse probability of censoring weights (IPCW) to assess the bias potentially induced by attrition during follow-up to D90. This method first estimates the probability of dropout to construct IPCWs, and then fits the GEE model with these IPCWs.

S3: Finally, logistic regression will be used to determine potential prognostic factors at baseline associated with LONG-COV at D90. The relationship between other variables including self-reported health, and LONG-COV will be assessed.

25. Adverse and Serious adverse events

Adverse events (AE), including serious adverse events (SAE), will be monitored and tracked using a logbook. They will be coded according to MedRA standards and will be summarized per intervention group.

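### SAP Section 24 tests LONG-COV at D14 and models it at Baseline and D14, where no definition in the SAP allows a positive status; D30 has no visit-specific rule

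*SAP*

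**What the plan says.** **Section 24 (analyses).** For objective S1 the SAP begins with description: "The presence and severity of symptoms at D14, D30 and D90 will be explored by doing a descriptive analysis for each study-time". It then adds a test: "The proportions of participants with LONG-COV at D14, D30 and D90 will be compared using the Cochran-Mantel-Haenszel test, adjusting for stratification". A by-arm summary follows: "A table will summarize the proportion of each symptoms at each time with the means severity per study arm". For S2, a GEE "will use Symptoms Severity as the outcome over all time points and include baseline characteristics". A supplementary logit GEE is then planned, "using a binary LONG-COV status as the outcome and including measurements at Baseline, D14, D30 and D90", with indicators for the stratification factors.

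**Section 20 (outcome definition).** For FLU-PRO symptoms: "A binome is a recurrent symptom, i.e. present at D30 and D90". The quality-of-life criterion likewise needs both visits. For functioning: "We selected participants with a non-zero value at D30 and a difficulty value at D90 higher than pre-COVID-19". Loss of taste or smell is the exception, since presence at either D30 or D90 is enough. Participants who meet a criterion go to physician review, potential cases are telephoned after the study, and the physician decides. Section 20 also cites a WHO definition set at 3 months after infection.

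**Section 7 (background).** "The long COVID is defined by the persistence of symptoms of the disease for more than 4 weeks after diagnosis". The questionnaires are dated from diagnosis.

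**Section 8 (objective S1).** The comparison wanted at D14, D30 and D90 is of the proportion of patients with COVID-19 symptoms, and of symptom severity. LONG-COV is not mentioned there.

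**The concern.** Section 24 treats LONG-COV as something observed at each visit. Section 20 treats it as one verdict per participant, reached after D90. If no participant can be positive at Baseline or D14, the D14 test has nothing to compare, and the supplementary GEE takes in visits whose outcome is either constant or undefined.

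Two things are at stake. First, the programmer must choose a coding for the early visits that the SAP does not give, and the reported GEE effect can depend on that choice. Second, the only stratified by-visit test of proportions in Section 24 is aimed at a different outcome from the one in objective S1.

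**Working it through.** **1. The plan's own figure.** The only computed size in the SAP is the primary sample size (Section 11: 50% versus 37.5%, two-sided alpha 5%, power 80%, 1:1). With pooled variance and no continuity correction:

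n = [1.960·√(2·0.4375·0.5625) + 0.8416·√(0.25 + 0.2344)]² / 0.125² = 246.1, rounded up to 247 per group, or 494 in total. Then 494/0.8 = 617.5, rounded up to 618.

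The figure reproduces and does not depend on the present point.

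**2. Days since diagnosis against each definition.** Four weeks is 28 days. Section 9 allows at most 10 days from diagnosis to inclusion.

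| Visit | Day | More than 28 days? | 3 months? | Used in Section 20? |
|---|---|---|---|---|
| Baseline | at most 10 | no (at least 18 short) | no | no |
| D14 | 14; at most 10 + 14 = 24 if counted from inclusion | no | no | no |
| D30 | 30 | yes (2 past) | no | only together with D90, except taste/smell |
| D90 | 90 | yes | yes | yes |

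Baseline and D14 fail every definition. D30 passes the 4-week definition, and taste or smell loss at D30 alone can send a participant to review. No rule, however, turns D30 data into a D30 status.

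**3. What the tests do with no positives.** With no events in either arm in any of the 8 strata (4 age groups × 2 genders), the CMH statistic is 0/0; a software check returned no value for the statistic or the p-value. In a simulated logit GEE with visit-by-arm terms and zeros at Baseline and D14, the visit coefficients for those two visits ran to about -29 to -33. They have no finite estimate, and those visits carry no treatment information.

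**4. Share of records affected (Section 16 flow chart).** The intervention arm has 307, 261, 251 and 240 participants with data at Baseline, D14, D30 and D90.

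- Total: 307 + 261 + 251 + 240 = 1,059.
- Baseline and D14: (307 + 261)/1,059 = 568/1,059 = 53.6%.
- Adding D30: 819/1,059 = 77.3% have no visit-specific rule.

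The other arm has 239 + 72 = 311 participants (239/311 = 76.8%, as printed), with 251 at D30 and 239 at D90. Its D14 count is not readable. Assuming 251 to 311, the Baseline-plus-D14 share runs from 562/1,052 = 53.4% to 622/1,112 = 55.9%.

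**5. How the coding moves the GEE (illustration only).** Assumptions: 247 per arm, D90 rates 37.5% and 50%, independence working correlation, cluster-robust standard errors, no time terms.

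| Assumed coding | Mean rate, probiotic / placebo | OR | z |
|---|---|---|---|
| D90 only, or D90 status carried back to all visits | 0.375 / 0.5 | 0.600 | -2.79 |
| Zero at Baseline and D14; D30 = D90 status | 0.1875 / 0.25 | 0.692 | -2.79 |
| Zero at Baseline, D14 and D30 | 0.09375 / 0.125 | 0.724 | -2.78 |

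For example, the last row is (0.09375/0.90625)/(0.125/0.875) = 0.1034/0.1429 = 0.724. If D30 had its own rule, with an assumed placebo rate of 50% to 80% and zeros at Baseline and D14, the OR would be 0.669 to 0.692 at a D30 risk ratio of 0.75, and 0.840 to 0.864 at a risk ratio of 1.0.

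**The case against.** The strongest defence is that LONG-COV in the S1 sentence is a slip for symptom presence. The sentences on either side of it are about symptoms, as is objective S1. An analyst would notice at once, because a 0/0 statistic is an obvious failure and not a misleading result. That is plausible, but the SAP would then name the wrong outcome in both the CMH sentence and the GEE sentence and would still need correcting. It would also not rescue Baseline: symptoms at inclusion are an eligibility criterion, so everyone would be positive there.

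A second defence reads the visit measurements in the supplementary GEE as model terms and not as repeated outcomes. The grammar allows this, but it is a strained reading for a method meant for repeated outcomes.

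A third is that objective S1 is served elsewhere. This is partly right. Section 24 has the descriptive analysis, the by-arm table and the S2 GEE, which may use a logit link and is meant to address the number as well as the severity of symptoms. Section 21 adds unstratified tests of individual symptoms, with no visit stated. None of these is a stratified by-visit test of the proportion with symptoms.

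Two further points stand. Section 11's remark about D30 or D90 concerns the scarcity of data on symptoms and sets no status. And z barely moves across codings of the same D90 status, so the odds ratios show ambiguity and do not measure harm to the trial.

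**Conclusion.** The concern holds. At D14 (CMH and GEE) and at Baseline (GEE), LONG-COV is undefined under Section 20 and negative for everyone under Section 7. At D30 a status is possible but has no rule. No reading makes all the listed visits usable as written: early visits coded negative make the D14 test degenerate, a carried-back status is constant over time and merely repeats the D90 comparison, and a symptom reading changes the endpoint.

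The 53.6% share rests on the printed intervention-arm counts and on reading the GEE as a repeated-outcome model; the range for the other arm rests on an assumed D14 count. The effect is limited to one secondary test and one supplementary model. The additional IPCW-weighted GEE would inherit the problem if it refits that model, which the SAP does not say. The primary D90 comparison and the sample size stand. The point should be fixed, but it does not threaten the trial's main conclusion.

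**What to change.** - **S1 test:** apply the stratified CMH at D14, D30 and D90 to a defined visit-level symptom indicator, for example at least one COVID-19 symptom, with the severity threshold stated.
- **Supplementary GEE:** use the same indicator at D14, D30 and D90 with visit and stratification terms, or drop this model. Leave Baseline out as an outcome, because eligibility makes everyone symptomatic there.
- **LONG-COV:** keep it as the single D90 outcome for Section 23 and S3. If a D30 status is wanted, write its rule into Section 20.

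The cost is a rewording of Section 24 and the reprogramming of one secondary test and one supplementary model, on data already collected.
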